4 STUDY DESIGN

This Phase 1/2 study will utilize a multicenter, open-label, dose-escalation design to evaluate the safety, efficacy, PK, and PD of FT-2102 administered orally to patients with AML or MDS.

Patients will be given FT-2102 daily (QD or BID) in continuous 28-day cycles, alone or in combination with azacitidine (administered at the dose of 75 mg/m² for 7 days IV/SC per every 28-day cycle) or LDAC (administered at the dose of 20 mg BID SC for 10 days every 28-day cycle) until treatment discontinuation. The term "study drug" will refer to either FT-2102, azacitidine or cytarabine.

Patients who discontinue for reasons other than disease progression/relapse or withdrawal of consent will continue to be followed for response until progression/relapse occurs.

Patients who achieve an adequate response to study treatment and meet other criteria required to undergo hematopoietic stem cell transplantation (HSCT) may proceed to HSCT after discontinuation of study treatment and will be followed on study for disease evaluation and any new HSCT conditioning or other new antineoplastic therapies received until disease relapse, death, withdrawal of consent, lost to follow-up, or end of study.

If a patient discontinues study drug to undergo HSCT, but is then deemed ineligible for HSCT, the patient may restart study drug with Medical Monitor approval.

Patients who undergo HSCT and then have persistent/recurrent IDH1-mutant (IDH1m) positive disease may be eligible to restart treatment with FT-2102 by re-enrolling in the appropriate Phase 2 cohort with Medical Monitor approval:

• Re-enrollment into Cohort 3 if morphologic relapse/progression

Patients who relapse post-HSCT and elect not to restart FT-2102 treatment will enter the overall survival follow-up period.

[figure not shown]
Patients participating in Phase 1 may be followed for survival for up to 12 months from C1D1 or for 28 days after treatment discontinuation (whichever is longer).

Patients participating in Phase 2 may be followed for survival for up to 36 months from C1D1 or for 28 days after treatment discontinuation (whichever is longer).

As shown in Figure 1, the study is comprised of 3 stages: a Phase 1 dose-escalation stage, a Phase 1 dose-expansion stage, and a Phase 2 stage.

Figure 1 Study Design

Phase 1 – Dose Escalation and Dose Expansion

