6.1.26 Survival Follow-up

After a patient discontinues or completes study treatment, the study site may be requested to contact the patient approximately every 3 months to collect survival status and data pertaining to any other alternative anti-neoplastic therapy. Patients enrolled in the Phase 1 dose-escalation/

dose-expansion stages may have survival follow-up performed for up to 12 months from C1D1 or 28 days after administration of last dose of drug (whichever is longer). Patients enrolled in the Phase 2 cohorts may have survival follow-up for up to 36 months from C1D1 or 28 days after administration of last study drug (whichever is longer).

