For a patient with none of these events before the end of study follow-up, EFS will be censored as per Table 1. For patients lost to follow-up prior to any evidence of event, the EFS data will be censored at their last completed assessment date that is SD or better prior to the initiation of anti-cancer therapy.

Overall survival (OS): OS is defined as the time in months from the first dose of study drug until death from any cause. For patients who are not known to have died by the end of study follow-up, OS will be censored on the date the patient was last known to be alive.

Transfusion independence (TI): Patients will be classified as "dependent" or "independent" at baseline within each category of platelets, pRBC, any (i.e., receiving either platelets or pRBC or both) and both (i.e., receiving both platelets and pRBC) if they received a transfusion within 8 weeks prior to the first dose of FT-2102. TI will be defined as patients who experience at least a 28-day or 56-day period during any point on treatment with no transfusion of that type required. For the "both" category, patients who are classified as dependent must have received both a platelet and pRBC transfusion within the 8 weeks prior to baseline, and to be classified post baseline as independent, they must experience a 28 or 56 day minimum duration on study where they did not require a transfusion of either platelets or pRBC.

B. Efficacy Analysis

Any response assessment occurring after the start of alternate anti-cancer therapy will not be included in the analyses using response assessments.

Note that some patients who were assigned to single agent therapy in Phase 1 requested to start combination therapy with azacitidine when a response was not observed on single agent treatment. In such cases, upon beginning dosing with azacitidine (if the patient was assigned to single agent therapy), then response assessments occurring after the first dose of azacitidine will not be included in efficacy analyses. Time to event analyses for such instances will be treated as if the patient has experienced disease progression when azacitidine is initiated.

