The overall survival and event-free survival analyses will be based on patients in the FAS. All other efficacy analyses will be based on patients in the EE analysis set as the primary analysis, with selected analyses on the FAS and PP analysis set as supportive. The following table indicates the analysis sets to be analyzed for each endpoint.

		A	alysis S	et
Endpoint	Patients Analyzed	EE*	FAS	PP*
CR/CRh Rate,				
DCR/CRh, TTCR/CRh	AML only	Х	Х	Х
CRR, DCR, TTCR	Each disease group separately	х	Х	Х
ORR, DOR, TTR	Each disease group separately	х	Х	х
Best overall Response	Each disease group separately	х	Х	Х
4-month RFS Rate	Phase 2 Cohort 2 only		Х	
RFS	Phase 2 Cohort 2 only		Х	
EFS, OS	All patients combined		Х	
TI	All patients combined	х	х	

*EE and PP analyses will only be performed for IA2.

CR/CRh rate will be analyzed for all cohorts except Phase 2 Cohort 2. For Phase 2 Cohort 1, to test the hypothesis that the CR/CRh rate is greater than 15%, a 1-sided exact test for a binomial proportion will be performed. If the exact one-sided p-value is less than 0.0245, the alternative hypothesis will be accepted. This is equivalent to at least 36 CR/CRh responses of 173 EE patients.

For Phase 2, Cohorts 3, 4, and 5 test the hypothesis that the 85% confidence interval for the CR/CRh rate does not include 10%. If there are 5 or more CR/CRh responses of the 20 patients in these cohorts, the 85% confidence interval will be greater than 10%, and the alternative hypothesis that the response rate is greater than 10% will be accepted.

Phase 2 Cohorts 6, 7, and 8 are Simon 2-Stage designs and the primary efficacy endpoint will be evaluated via the number of CR/CRh responses stipulated in the design criteria described in Section IV.C.

The number and proportion of patients achieving CR/CRh response will be reported by cohort from the binomial proportion, along with Clopper-Pearson 95% confidence interval for AML and MDS patients respectively. Appendix 2 provides the SAS code.

For Phase 2 Cohort 1, a sensitivity analysis will be performed on the CR/CRh rate in which Atkinson and Brown confidence intervals will be calculated.

4-Month RFS, BOR, ORR, TI: The proportional endpoints listed here will be summarized as the number and percentage of patients within each category, and will be presented by cohort along with Clopper-Pearson 95% confidence intervals. The 4-month RFS endpoint will be analyzed for Phase 2 Cohort 2 only.

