RFS, EFS, OS, TTCR/CRh, TTCR, TTR, DCR/CRh, DCR, DOR: Time to event endpoints listed here will be expressed as the number of months from first dose to the event and will be analyzed using Kaplan-Meier (KM) methods for each cohort, with the exception of TTCR/CRh, TTCR, and TTR, since these analyses are performed only on the subset of responders and censoring is unnecessary. The analysis will include median, 1st and 3rd quartiles for time calculated using Kaplan-Meier methods, and the 95% confidence interval for the median

calculated using the Brookmeyer-Crowley method. The estimated probability of survival over time for RFS, EFS, OS, DCR/CRh, DCR, and DOR will be plotted as KM curves for Phase 2 Cohort 1, with the exception of RFS, which will be performed for Phase 2 Cohort 2 only. Appendix 2 provides the SAS code.

The survival probability and 95% confidence interval will be estimated at selected landmark timepoints of: 3 months, 6 months, 12 months, and 24 months based on Kaplan-Meier product-limit method and Greenwood's formula. A month will be calculated as time in days divided by 30.4375.

Table 1. Censoring Rules

Case	Censoring Rule
Patient has no post baseline assessments	Censor at date of first dose
and no date of death recorded	
Patient did not die or experience PD or	Censor at date of last adequate response
relapse*	assessment (any response assessment that is
	not "Not Evaluable" or "Not Done")
Patient in Phase 1 started on single agent	Censor at date of last adequate response
therapy, but switched to combination	assessment prior to the combination therapy
therapy	

*For patients who discontinue FT-2102 treatment to receive HSCT and remain on study to be followed until documented disease relapse, confirmation of relapse is not required in this situation, and a single occurrence of relapse will be considered as documented "confirmed" relapse in analyses of response.

The following sensitivity analyses of DCR/CRh will be performed with censoring rule variations in EE patients:

- 1. Patients who undergo HSCT will be censored at the last adequate assessment prior to HSCT
- 2. Patients who discontinued study treatment due to undocumented progression will be considered as events at the date of last dose
- 3. Patients with subsequent anti-cancer therapies prior to an event date will be considered to be censored the day before the start of the anti-cancer therapy.

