- ^w EQ-5D-5L survey can be completed anytime during screening prior to C1D1 dose.
- x Study drug diary should be distributed by the site to the patient on each cycle day 1, and collected at the next cycle day 1 visit

- ^y Single agent (FT-2102): FT-2102 will be given in accordance with dosing schedule × 28 days out of 28 days. On C1D1 only a single dose of FT-2102 is taken.
- ² Combination agent (FT-2102 + azacitidine): azacitidine will be administered via subcutaneous injection or intravenous infusion in combination with oral FT -2102 for 7 days, and then azacitidine will be stopped for 21 days; a 48-hr dose interruption of the azacitidine for weekends or holidays is allowed. On C1D1 and C2D1, azacitidine is to be administered immediately prior to FT-2102 (to enable consistent PK assessments). On all other days and cycles when FT-2102 and azacitidine are co-administered, it is recommended to dose FT-2102 prior to azacitidine.
- ^{aa} Combination FT2102 + cytarabine: cytarabine will be administered at a dose of 20 mg BID subcutaneously (SC) for 10 days every 28-day cycle
- ^{bb} After a patient discontinues study treatment and has completed their last study treatment visit, the study site will contact the patient approximately every 3 months to collect survival data and data pertaining to any other alternative anti-neoplastic therapy the patient begins for up to 12 months from the time of their 1st dose of study drug. Patients who discontinue for reasons other than disease progression or who withdraw consent will continue to be followed for response until progression occurs.
- * Not required in Phase 2 unless patient is participating in 24-hour Holter monitoring.
- ** Not required in Phase

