Appendix 3 Column Headings for Analysis Tables

1. Data snapshots taken for the purpose of safety analysis (regulatory reporting, IB update, etc.) will be organized as follows:

Note: to be performed on data from both phase 1 and phase 2 patients, regardless of cohort #

2. Table generation for interim futility and efficacy analyses as well as final analyses will be organized as follows:

Phase 1:

Table xxx: Title xxx Analysis Set, Phase 1

	Single Agent		Combination: Azaci	Combination: Azacitidine 75 mg/m ² $$		
	FT-2102	Total	FT-2102	Total	Phase 1	
Parameter	150 mg BID	FT-2102	150 mg BID	FT-2102	Overall	

For Safety Tables:

Phase 2 Single Agent Therapy:

Table xxx: Title xxx Analysis Set, Phase 2 Single Agent

			FT-	-2102 150 mg H	BID	
					Phase 2	
					Single Agent	Ph.1 AML R/R
Parameter	Cohort 1	Cohort 2	Cohort 3	Cohort 7	Overall	& Ph.2 Cohort 1

Phase 2 Combination Therapy:

Table xxx: Title xxx Analysis Set, Phase 2 Combination Therapy

		FT-2102 150	mg BID + Azacitid	ine 75 mg/m²	
					Phase 2 Combination Therapy
Parameter	Cohort 4	Cohort 5	Cohort 6	Cohort 8	Overall

For Efficacy Tables:

Phase 2 Single Agent:

Table xxx: Title xxx Analysis Set, Phase 2 Single Agent

	FT-2102 150 mg BID				
Parameter	Cohort 1	Cohort 2	Cohort 3	Cohort 7	Ph.1 AML R/R & Ph.2 Cohort 1

Phase 2 Combination Therapy:

Table xxx: Title xxx Analysis Set, Phase 2 Combination Therapy

FT-2102 150 mg BID + Azacitidine 75 mg/m²

Parameter	Cohort 4	Cohort 5	Cohort 6	Cohort 8

DocuSign

Timestamp

Certified Delivery Events

Status

Carbon Copy Events	Status	Timestamp	
Witness Events	Signature	Timestamp	
Notary Events	Signature	Timestamp	
Envelope Summary Events	Status	Timestamps	
Envelope Sent	Hashed/Encrypted	2/19/2023 7:01:45 PM	
Certified Delivered	Security Checked	2/20/2023 3:01:41 PM	
Signing Complete	Security Checked	2/20/2023 3:02:20 PM	
Completed	Security Checked	2/20/2023 3:02:20 PM	
Payment Events	Status	Timestamps	
Electronic Record and Signature Disclosure			

CONSUMER DISCLOSURE

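### Phase 1 overall survival at 24 months cannot be read reliably, because after month 12 survival follow-up depends on whether and why the patient has stopped treatment

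*SAP*

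**What the plan says.** **Analysis.** SAP Section XI.B bases OS on the Full Analysis Set ("The overall survival and event-free survival analyses will be based on patients in the FAS"), which covers both phases. It says that the time-to-event endpoints "will be analyzed using Kaplan-Meier (KM) methods for each cohort", with medians and quartiles, and then: "The survival probability and 95% confidence interval will be estimated at selected landmark timepoints of: 3 months, 6 months, 12 months, and 24 months". The OS code in SAP Appendix 2 repeats the 24-month point. Protocol Section 9.2.4.3 also asks for landmark OS in all cohorts. SAP Section XI.A gives the censoring rule: "OS will be censored on the date the patient was last known to be alive".

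**Tables.** SAP Appendix 3 lists a Phase 1 table among the layouts for interim and final analyses. Its single-agent efficacy layout for Phase 2 includes a pooled column, "Ph.1 AML R/R & Ph.2 Cohort 1".

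**Follow-up.** Protocol Section 4 says: "Patients participating in Phase 1 may be followed for survival for up to 12 months from C1D1 or for 28 days after treatment discontinuation". The later of these two dates applies. Section 6.1.26 repeats the rule. Phase 2 patients may be followed to 36 months.

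**SAP schedule.** Footnote bb in SAP Appendix 1 has survival contact continuing "for up to 12 months from the time of their 1st dose of study drug", with no distinction by phase.

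**The concern.** Kaplan-Meier estimation assumes that patients censored at a given time have the same prognosis as those who remain at risk. Up to month 12 the Phase 1 rule respects this, because no one is administratively censored before then. After month 12 it does not. A patient who progressed, stopped early and is alive at month 12 leaves the risk set. A patient still on drug stays in it, and leaves about four weeks after stopping. The curve beyond month 12 is then driven by a selected group, and the estimator applies that group's survival to everyone alive at month 12.

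What is at stake is the Phase 1 24-month OS figure, and any median or quartile that falls beyond 12 months. The only OS sensitivity analysis in the SAP concerns COVID-19 deaths, so nothing planned would show the problem.

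**Working it through.** The documents give no OS rates, event counts or power, so there is no figure of the plan's to reproduce. The check sets the follow-up rule against the landmarks and then sizes the effect by simulation under stated assumptions.

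**Step 1: who is still followed after month 12.** For Phase 1, censoring time = max(12 months, stopping time + 28 days). With the SAP's month of 30.4375 days, 28 / 30.4375 = 0.92 months. A patient who stops before 12 − 0.92 = 11.08 months and is alive at month 12 is censored there. The exception is a patient who stops without progression, including for stem cell transplantation (HSCT). Protocol Sections 4, 6.1.25 and 8.2.1 keep following these patients for response until relapse, with no 12-month cap.

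**Step 2: what the estimator does.** The estimate at 24 months is S(12) × the survival from 12 to 24 months observed in those still followed. The first factor is sound; the second comes from the selected group.

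**Step 3: size, Phase 1 alone.** All rates below are assumptions.

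- *Model A* (200,000 patients per scenario): 35% responders with median time on drug 12 months, others 3 months; 15% stop because of death; median survival after stopping 4 months; no HSCT route.
- *Model B* (400,000 patients per scenario): mean 6 months to stopping for reasons other than death, prompted by the protocol's expected treatment duration of about 26 weeks; 0 or 15% long stayers with mean 24 months; median survival on treatment 18 to 36 months, and 4 to 8 months after stopping (24 months for both when hazards are equal); 0 or 10% HSCT, with HSCT patients followed to relapse.

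| Scenario | S(12) true / KM | S(24) true | S(24) KM | Bias (points) |
|---|---|---|---|---|
| A, base case | 0.410 / 0.410 | 0.151 | 0.325 | +17.4 |
| B, medians 24 on, 8 off | 0.489 / 0.489 | 0.186 | 0.317 | +13.1 |
| B, 18 on, 6 off (smallest with unequal hazards) | 0.391 / 0.391 | 0.110 | 0.215 | +10.4 |
| B, 36 on, 4 off, long stayers and HSCT (largest) | 0.410 / 0.410 | 0.127 | 0.292 | +16.6 |
| B, equal hazards, no HSCT or long stayers | 0.706 / 0.706 | 0.499 | 0.496 | −0.3 |

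Bias is taken from the unrounded values, so it can differ by 0.1 from the columns.

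Variants of Model A (median survival after stopping 4 to 10 months, responder time on drug 12 to 18 months) give about 17 to 20 points. Across Model B the bias is 10.4 to 16.6 points with unequal hazards and −0.3 to +1.4 with equal hazards.

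Step 2 shows where the error enters. In the second row the true survival from 12 to 24 months is 0.186 / 0.489 = 0.38, and the estimator uses 0.317 / 0.489 = 0.65. In Model A's base case, 56% of those alive at month 12 stay in follow-up and 79% of these are responders, against 35% at entry.

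**Step 4: quantiles.** In Model A's base case true survival passes 25% between month 12 (41.0%) and month 24 (15.1%), so the true third quartile lies before month 24. The Kaplan-Meier curve is still at 32.5% at month 24. The median is unaffected there, because S(12) is already below 50%.

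**Step 5: pooled column.** The Phase 1 share is not given. Single-agent expansion allows up to 14 patients in each of up to two cohorts, with at least 6 more from escalation, so 14 + 6 = 20 and 28 + 6 = 34 are reasonable working numbers beside about 190 in Cohort 1. In Model B the pooled bias at 24 months is at most 0.5 points with 20 Phase 1 patients, 0.9 with 34 and 1.6 with 60. Model A gives 1 to 2 points if Phase 1 makes up 20% of the column. The effect is small because few Phase 1 patients remain at risk. In the second row of the table 23% of those alive at month 12 are still followed, so 34 Phase 1 patients form (34 × 0.23) / (34 × 0.23 + 190) = 7.8 / 197.8 = 4% of the pooled risk set just after month 12.

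**The case against.** Several objections carry weight.

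**Other routes past month 12.** A reader might infer that only patients still on treatment are followed after month 12. The documents do not support that. Besides the 28-day extension, patients who stop without progression are followed to relapse, and HSCT patients until relapse or death. Some single-agent patients who progress may also re-enrol in Cohort 6, and some who relapse after HSCT in Cohort 3, both with Phase 2 follow-up. The first two groups are favourable, so including them does not remove the selection; Model B includes the HSCT route and still shows the bias. Re-enrolment is in neither model and could reduce the bias if later survival dates were carried back to the Phase 1 record, which the SAP does not address.

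**Direction and size.** A reader might take the upward bias as established. It needs a higher death hazard off treatment than on it, and the documents give no rates. Treatment failure is a listed reason for stopping, which makes this plausible, but it remains an inference. Model A also implies a mean time on drug of (0.35 × 12 + 0.65 × 3) / ln 2 = 8.9 months, longer than the protocol's 26 weeks; Model B, set closer to that figure, gives the lower part of the range.

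**Importance.** OS is not a listed Phase 1 endpoint (Protocol Section 3, SAP Section III), secondary endpoints are descriptive, and OS curves are planned for Cohort 1 only. This is right. The problem would appear in tables and no decision rule depends on it.

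**Footnote bb.** A reader might infer that its 12-month limit biases Phase 2 OS. It does not by itself. The SAP says it is based on protocol version 5, and the current protocol, including its own schedule footnotes, gives Phase 2 patients 36 months. The footnote looks like outdated text.

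**Conclusion.** The mismatch stands on the documents alone: a 24-month landmark is requested without limit by phase, while Phase 1 survival follow-up beyond month 12 depends on treatment status and reason for stopping. Whether this inflates the result depends on the hazards. With higher mortality off treatment, Phase 1 24-month OS and quantiles beyond 12 months are overstated, by roughly 10 to 20 points under the rates assumed here; with equal hazards the bias is about zero. Phase 1 landmarks at 3, 6 and 12 months, and medians below 12 months, are unaffected.

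A reader might conclude that the pooled column is also seriously distorted. The arithmetic does not support that: about 0 to 2 points, because Cohort 1 dominates the late risk set. Removing all pooled OS after 12 months would be out of proportion. Footnote bb is a separate inconsistency that must be reconciled, and is not evidence of biased Phase 2 survival.

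**What to change.** 1. In SAP Section XI.B, censor Phase 1 OS administratively at 12 months from first dose. For Phase 1, do not report the 24-month landmark or any quantile beyond 12 months.
2. In SAP Appendix 3, keep the pooled column but footnote that its two parts have different survival follow-up, and take OS after 12 months primarily from the separate Cohort 1 column.
3. Reconcile footnote bb in SAP Appendix 1 with the protocol's 36-month survival follow-up for Phase 2.

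The cost is SAP wording, one censoring rule and one table footnote. No new data are needed. The downside is that no Phase 1 24-month OS is reported.

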Transfusion independence, defined as the proportion of patients who have received a packed red blood cell or platelet transfusion in the eight weeks prior to first dose of FT-2102 who have a 28-day period during any point on study with no transfusion required. Additionally, the number of patients who are transfusion independent for at least 56 consecutive days will also be summarized. Percent of transfusion independence will be calculated based on the number of patients who were transfusion dependent prior to first dose of FT-2102.

For each cohort, the number and percentage of the best overall response will be presented by response category and by treatment group. Other binomial endpoints including overall response rate (CR + CRh + CRi + MLFS + PR) and rate of responses in the individual response category, will also be analyzed. Number and percentage of patients within each response category will be presented by dose/dosing schedule and visit. Clopper-Pearson 95% confidence intervals will be provided along with the responses.

Overall survival for all cohorts at landmark timepoints will be analyzed.

Time to event data will be analyzed using Kaplan-Meier (KM) methods for each cohort. The median time will be tabulated along with the 95% Brookmeyer Crowley confidence intervals. The estimated probability of survival over time will be plotted as KM curves for each cohort (or by disease type and by treatment).

Detailed considerations for all time to event variables are provided in the SAP.

Additional efficacy analyses will be specified in the SAP.

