Subgroup Name	Levels	Additional Details, if applicable		
		(140 - age) * baseline weight (kg) * (0.85 if		
		female) /		
		(72 * baseline serum creatinine [mg/dL])		

K. Data Display Characteristics

Data displays produced for this study will include three types—summary tables, data listings, and figures. Unless stated otherwise, data listings will be produced for all recorded data as well as derived variables. Summary tables will be produced as specified in following sections. Figures will be produced when specified in sections to follow.

Listings will be ordered by phase, treatment (dose and schedule), cohort, patient number, and nominal visit. When expedient, additional levels of ordering hierarchy may reflect subsets of assessments within patient. Data listings will not display patient initials.

Tables will be organized differently based on the purpose of the data analysis being performed: interim safety analyses or formal interim analysis or final analysis. Data snapshots taken for the purpose of safety analysis (regulatory reporting, IB update, etc.) will be organized as outlined in Appendix 3. Table generation for interim futility and efficacy analyses as well as final analyses will be organized as specified in Appendix 3.

The summary statistics displayed will be a function of the type of data associated with the summarized assessment. Unless stated otherwise in relevant sections to follow, continuous data will be summarized with the number of non-missing values, mean, standard deviation, minimum, median, and maximum. Categorical data will be summarized with the number of non-missing values and the numbers of values equal to each of the possible values. Percentages of patients with each of the possible values will be calculated from the number of patients in the corresponding analysis set, unless stated otherwise. Some continuous variables may also be grouped into categorical levels and evaluated in frequency tables.

L. Blinded Review of Data

Not applicable for this study, as it is open label.

VII. Baseline Patient Characteristics and Disposition

A. Disposition

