- 4. Patients with subsequent anti-cancer therapies prior to an event date will be considered as having an event as the start of the anti-cancer therapy.
- 5. Patients who didn't have an event and are still on treatment will be censored at the last treatment date, otherwise will be censored at the last response assessment.

For DOR and DCR HSCT sensitivity analysis will be performed, where patients who undergo HSCT will be censored at the last adequate assessment prior to HSCT. The following subgroup analyses will be performed:

• CR/CRh rate, ORR, DCR/CRh – For AML patients in the EE analysis set: AML type (primary or secondary), disease state (relapsed/refractory or treatment naive), AML cytogenetic risk classification, IDH1 mutation type, IDH1 mutation confirmed by

central lab, age group, sex, region, race, baseline ECOG PS, prior HSCT for AML, prior HMA, prior IDH1 therapy, and prior FT-2102 therapy.

• OS, EFS – For AML patients in the FAS analysis set: AML type (primary or secondary), disease state (relapsed/refractory or treatment naive), AML cytogenetic risk classification, IDH1 mutation type, IDH1 mutation confirmed by central lab, age group, sex, region, race, baseline ECOG PS, prior HSCT for AML, prior HMA, prior IDH1 therapy, and prior FT-2102 therapy.

Kaplan Meier plots will not be produced for subgroup analyses.

Transfusion Independence

Transfusion independence will be analyzed as part of the clinical benefit expected from FT-2102. The percentage of patients who are transfusion dependent at baseline will be summarized (overall and by type of blood product of RBC and/or platelets). The proportion of patients who became transfusion independent during any 28-day and 56-day period during treatment will be summarized by best overall response on study. Percentages will be based on the number of patients within the best overall response category.

Swim Lane Plot of Time on Treatment and Duration of Response

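### The SAP bases its by-response transfusion-independence percentages on everyone in the response category; the protocol bases them on patients who were transfusion dependent before first dose

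*SAP*

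**What the plan says.** **Protocol 9.2.4.3** (secondary efficacy endpoints) defines TI as "the proportion of patients who have received a packed red blood cell or platelet transfusion in the eight weeks prior to first dose" and who then have a qualifying transfusion-free period. It goes on to fix the denominator: "Percent of transfusion independence will be calculated based on the number of patients who were transfusion dependent prior to first dose of FT-2102".

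**SAP XI.A** classifies each patient at baseline as dependent or independent for four product categories: platelets, pRBC, any and both. Its general definition of the endpoint is: "TI will be defined as patients who experience at least a 28-day or 56-day period during any point on treatment", without a transfusion of that type. That sentence does not require baseline dependence. Only the *both* category mentions it: "patients who are classified as dependent must have received both a platelet and pRBC transfusion within the 8 weeks prior to baseline".

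**SAP XI.B, Transfusion Independence**, plans three things in sequence:
- "The percentage of patients who are transfusion dependent at baseline will be summarized", overall and by blood product.
- "The proportion of patients who became transfusion independent during any 28-day and 56-day period during treatment will be summarized by best overall response".
- The denominator for that breakdown: "Percentages will be based on the number of patients within the best overall response category".

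**SAP XI.B, earlier in the section**, also plans TI by cohort as a number and percentage with Clopper-Pearson 95% intervals, and names no denominator. **SAP VI.K** gives the default: percentages "will be calculated from the number of patients in the corresponding analysis set, unless stated otherwise".

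**The concern.** The question of interest is how many patients who needed transfusions stopped needing them. A patient who was not dependent at baseline cannot make that change. Placing such patients in the denominator turns a conversion rate into a quantity that also depends on case mix.

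The SAP presents TI as part of the drug's expected clinical benefit, and the table is laid out by best overall response, so it invites comparison between categories. If baseline dependence differs between categories, the percentages can differ even when the conversion rate is the same. The SAP states that it governs the analysis, so a programmer following it would produce a percentage that is not the protocol's endpoint.

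**Working it through.** The plan states no target or expected TI rate, so there is no figure to reproduce. The check has two parts: compare the texts, then see how far the two denominators can differ.

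**1. Does anything in the SAP restore the protocol denominator?**
- XI.A derives baseline status but does not name it as the denominator. Its general definition covers any patient with a long enough transfusion-free period.
- The endpoint table in XI.B lists TI for all patients combined. In that column the contrast is with endpoints analysed separately by disease group, so the entry says nothing about baseline dependence and adds no restriction.
- The default in VI.K is the analysis set.

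So nothing restores it.

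**2. Formulas.** For one response category, let
- d = share dependent at baseline,
- c = conversion rate among dependent patients,
- m = share of baseline-independent patients with a qualifying transfusion-free period.

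Then
- Protocol: c
- SAP, reading A (numerator is dependent converters only): c × d
- SAP, reading B (numerator is anyone with a transfusion-free period, as in the general XI.A definition): c × d + m × (1 − d)

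The documents give none of d, c or m. Every value below is an assumption.

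**3. Worked case, d = 0.6 and c = 0.4.**
- Protocol: 40%
- Reading A: 0.4 × 0.6 = 24%
- Reading B, m = 0.6: 0.24 + 0.6 × 0.4 = 48%
- Reading B, m = 1.0: 0.24 + 1.0 × 0.4 = 64%

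**4. Over a wider assumed range.**

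| d | Protocol (c) | SAP, A | SAP, B (m = 0.6 to 1.0) |
|---|---|---|---|
| 0.4 | 30% | 12% | 48% to 72% |
| 0.4 | 70% | 28% | 64% to 88% |
| 0.8 | 30% | 24% | 36% to 44% |
| 0.8 | 70% | 56% | 68% to 76% |
| 1.0 | c | c | c |

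Reading A understates c by the factor d. Reading B exceeds c when m > c and falls below it when m < c; at d = 0.4, c = 70% and m = 0.6 it gives 64%. Agreement is guaranteed only when everyone in the category was dependent at baseline.

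**5. Comparison between categories.** Take c = 50% in two categories, with d = 0.4 in one and d = 0.8 in the other. The protocol gives 50% in both.
- Reading A: 0.5 × 0.4 = 20% against 0.5 × 0.8 = 40%
- Reading B, m = 1.0: 0.20 + 0.60 = 80% against 0.40 + 0.20 = 60%
- Reading B, m = 0.6: 0.20 + 0.36 = 56% against 0.40 + 0.12 = 52%

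Equal conversion appears as a difference, and its sign depends on the numerator chosen.

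**The case against.** The best defence is the verb in the SAP's numerator. Patients who *became* independent must have been dependent before, and XI.A has already classified everyone at baseline. On that view the denominator sentence means only that percentages are taken within each response category, among patients who could convert. This reading is possible, but it does not rescue the text. The denominator sentence names a different group, although dependence at baseline is spelled out two sentences earlier, and the general XI.A definition does not require it.

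A reader might also take the change to be deliberate, since the SAP's summary of changes records an edit to the TI analysis in version 2.0. The entry does not say what was edited, mention the denominator or declare a departure from the protocol.

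Several limits on the point do stand:
- A reader might infer that every TI percentage in the SAP uses the response-category denominator. The sentence governs only the by-response table. The cohort-level percentages have no stated denominator, which is a gap of a different kind.
- A reader might infer that the plan overstates the benefit. The documents fix no direction, and the upper figure of 64% needs every baseline-independent patient to stay transfusion-free and be counted.
- Correcting the denominator does not make response categories cleanly comparable. Protocol Appendix 7 makes transfusion independence a criterion for CR in AML, so TI and best response are linked by definition.
- The SAP also reports baseline dependence overall and by product. This gives some context, but no split by response category is stated.

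**Conclusion.** The point holds for the by-response TI table, which is wrong as written. The two documents state different denominators for the same endpoint, and the SAP neither restores the protocol's nor explains the change. The cohort-level TI percentages and intervals need the same denominator stated, because the SAP leaves it open there.

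The size is illustrative only. In the worked case a 40% protocol rate becomes 24%, or 48% to 64%, depending on who is counted in the numerator. Those figures rest on the assumed shares and would change with them.

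The consequence is confined to a secondary endpoint. SAP VI.H treats secondary endpoints as descriptive, and TI carries no hypothesis, power or stopping rule. The primary CR/CRh test, the interim rules and the sample sizes are untouched.

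**What to change.** 1. In SAP XI.B, replace the denominator sentence with: *For each product category (platelets, pRBC, any, both), percentages are based on the number of patients within each best overall response category who were transfusion dependent for that category at baseline.* The product wording matters. Without it, a patient dependent on pRBC only could enter the platelet denominator and recreate the problem.
2. Apply the same product-specific, baseline-dependent denominator to the cohort-level TI percentages and their Clopper-Pearson intervals in XI.B.
3. Report maintained independence among baseline-independent patients as a separate row or table.
4. If the response-category denominator was intended, say so, give the reason for departing from protocol 9.2.4.3, and still show the protocol-defined percentage.

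The cost is a few sentences and a table-shell change. Baseline status by product is already derived in XI.A, so no new data are needed. Denominators will be smaller and intervals wider, which reflects the information actually available on conversion. If the database is already locked, the SAP's introduction requires the change to be documented in the study report as a deviation.
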